- Ability to understand and willingness to sign a written informed consent and HIPAA consent document

Exclusion criteria

- Inability or non-willingness to provide informed consent
- Failure to comply with the study protocol
- Patients with known allergy for fluorescein or risk factors for an allergic reaction
- Use of beta-blocker within 24 hours before the start of the bronchoscopic procedure
- Possibly pregnant, pregnant or breastfeeding women
- Patients with hemodynamic instability
- Patients with refractory hypoxemia
- Patients with a therapeutic anticoagulant that cannot be held for an appropriate interval before the procedure
- Patients who are unable to tolerate general anesthesia according to the anesthesiologist
- Patient undergoing chemotherapy

Intra-operative Exclusion/Stopping Criteria:

- The lesions are unable to be localized/confirmed by bronchoscopy
- The procedure will be terminated if the patient develops a significant procedural complication as determined by the treating physician
- The procedure will be terminated if the patient develops hemodynamic instability as determined by the treating physician

Sample size calculation

A bronchoscopic TBNA (Robotic-guided TBNA or Robotic-nCLE-guided TBNA) will be regarded as successful when histological confirmation of the diagnosis is achieved and matches the final diagnosis. If additional TBNA passes or tests, e.g., further bronchoscopies, surgery, etc., are needed to establish the diagnosis, the TBNA pass will be regarded as non-diagnostic.

We will calculate TBNA diagnostic yield for the cumulative number of passes until five cumulated passes for both the Robotic-guided TBNA and Robotic-nCLE-guided TBNA arms. It is anticipated that sequential passes at a target site will result in stepwise yield increments to a plateau. Every needle pass at a location will be reported separately and entered into a database to provide yields after each sequential pass.

Proportional data will be compared using a Chi-squared test of contingency tables or Fisher's exact test on 2x2 contingency tables in the case of very small counts (<5).

First- and cumulative-pass diagnostic yields:

Diagnostic yields for the different cumulative passes are defined as follows:

1. First-pass diagnostic yield is calculated as the proportion of patients for which first-pass TBNA during the bronchoscopic procedure yielded a definitive diagnosis out of the total number of patients that have received a diagnostic procedure.

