The tumor board will determine intermediate diagnosis and management recommendations for each patient at the intermediate and final diagnosis phases (see Figure 3). Three therapeutic management options will be considered: "neither treatment nor follow-up", "follow-up", or "treatment" (see above). If the diagnosis is certain, "neither surgery nor surveillance" will be recommended for benign nodules; treatment will be recommended for malignant lesions; either treatment or follow-up will be recommended for indeterminate nodules.

An intermediate diagnosis and an intermediate management recommendation will be provided after the tumor board receives TBNA histological results and recorded in the Case Report Form for each patient of both arms.

A final diagnosis and a final management recommendation will be provided just after the final diagnosis results are received by the tumor board and recorded in the Case Report Form for each patient of both arms.

These intermediate diagnosis and management recommendations will also be compared to the definitive diagnosis and final patient management decisions.

7. Statistical Analysis

Population demographics comparison in both arms:

Statistical analysis will be performed to compare the patient population in terms of demographics to assess whether there are any differences between the populations of the two arms in terms of age, sex, race, type of lung cancers, and cancer prevalence.

Lesion characteristics comparison in both arms:

Statistical analysis will be performed to compare the lesion characteristics to assess whether there is any difference in lesion characteristics between the two arms, in terms of size, location of the nodule, Presence of bronchus sign on computerized tomography, lung zone, positive PET, associated lymphadenopathy, distance closest to fissure, distance from lesion to pleura, and pre-procedure probability of malignancy.

Navigation Accuracy

Distance between the tip of the locatable guide/nCLE Confocal MiniprobeTM and the targeted lung lesion will be measured for each nodule. The median and standard deviation of the distance will be calculated for both arms. Using a statistical test (Student T-test), they will be compared between arms (Robotic-guided TBNA and Robotic-nCLE-guided TBNA).

Navigation success

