Based on investigator self-assessment, the proportion of cases in which the operator can successfully navigate to the lung target with Robotic guidance and Robotic-nCLE guidance will also be recorded and compared for both arms. Using a statistical test (Student T-test), the navigation success will be compared between arms (Robotic-guided TBNA and Robotic-nCLE-guided TBNA).

Navigation time

Total time that the locatable guide/ nCLE Confocal MiniprobeTM is used in the subject during the Robotic-guided TBNA or Robotic-nCLE-guided TBNA procedure. The navigation time medians and standard deviations will be calculated for both arms. Using a statistical test (Student T-test), they will be compared between arms (Robotic-guided TBNA and Robotic-nCLE-guided TBNA).

First- and cumulative-pass diagnostic yields and performance calculations

First-pass diagnostic yield was defined above (see section Sample size calculation for the definition). Two first-pass diagnostic yields will be calculated one for the Robotic-nCLE-guided TBNA arm and a second one for the Robotic-guided TBNA arm. 95% confidence intervals will be calculated, and the p-value to compare diagnostic yield values between the two arms. Sequential cumulative pass diagnostic yields will also be calculated for each arm.

The diagnostic performance of the sequential cumulative ROSE passes and the sequential cumulative nCLE passes for the Robotic-nCLE-guided TBNA arm and of ROSE only for the Robotic guided TBNA will also be assessed at the end of a follow-up period according to their sensitivities, specificities, positive predictive value (PPV), and negative predictive value (NPV). The sensitivity test will measure the ability of sequential cumulative ROSE passes or sequential cumulative nCLE passes to characterize malignant nodule (true positive rate) correctly. In contrast, the specificity test will measure the ability for sequential cumulative ROSE passes or sequential cumulative nCLE passes to correctly characterize benign nodule (true negative rate) using the final/definitive diagnosis as the reference.

Where a = true positive, b = false positive, c = false negative, and d = true negative:

- Sensitivity: Probability that sequential cumulative ROSE passes will be positive when malignancy is present (true positive rate): $= a/(a + c)$

- Specificity: Probability that a sequential cumulative ROSE passes will be negative when malignancy is not present (true negative rate): $= d/(b + d)$

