- Accuracy: Probability that a Robotic-guided biopsy gives correct prediction among the total number of cases examined: $= (a + d)/(a + b + c + d)$

Patient diagnostic and management analysis:

Intermediate and final diagnosis and management recommendation proportion differences for the two patient populations (Robotic-guided TBNA arm and Robotic-nCLE-guided TBNA arm) will be compared using a chi-square test. Intermediate and final diagnosis and management recommendation proportions will also be compared for the two patient populations. Differences between Robotic-guided TBNA and Robotic-nCLE-guided TBNA arms regarding the specific diagnostic and management categories will be compared using McNemar's test both at the intermediate diagnosis and the final diagnosis stage.

Feasibility statistical analysis:

The feasibility of needle-based lung cancer diagnosis will be assessed by investigating the following items:

- Assessing nCLE-image quality
- Assessing the feasibility of the integrated needle/Cellvizio® I.V.E Confocal Miniprobe™.

The imaging feasibility yield for the Robotic-nCLE-guided TBNA procedure is defined as the proportion of patients in whom procedure will yield at least good nCLE image quality out of the total number of patients that will receive that procedure.

The mechanical feasibility yield for the Robotic-nCLE-guided TBNA procedure is defined as the proportion of patients for whom Robotic-nCLE-guided TBNA procedure will be possible mechanically (meaning that the nCLE probe will be guided to the nodule successfully) out of the total number of patients that will receive that procedure.

Safety:

The safety will be assessed by carefully monitoring adverse events related to both procedures. Serious adverse event rates will be calculated by dividing the number of events for each procedure divided by the total number of procedures for each arm.

Reproducibility:

To assess the reproducibility of bronchoscopy guided nCLE:

- Estimating the reproducibility of nCLE criteria will be evaluated by calculating the inter-observer agreement of nCLE criteria between 3 readers (Fleiss Kappa).

In Wijmans et al. [10], three nCLE characteristics for the detection of malignancy were identified in different subtypes of lung tumors and metastatic lymph nodes:

- 1) dark enlarged pleomorphic cells;
- 2) dark cell clusters consisting of overlapping cell structures ('dark clumps'); and

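### Navigation success, a proportion, is assigned a Student t-test against the plan's own chi-square/Fisher rule, and medians of navigation time and distance are paired with a test of means (minor)

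*Combined protocol and SAP*

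**What the plan says.** All references are to the combined protocol and SAP.

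- **Section 7, Navigation success.** The outcome is "the proportion of cases in which the operator can successfully navigate to the lung target", judged by the investigator. The test is given as: "Using a statistical test (Student T-test), the navigation success will be compared between arms".
- **Section 4, Sample size calculation.** A general rule reads: "Proportional data will be compared using a Chi-squared test of contingency tables or Fisher's exact test on 2x2 contingency tables", the latter "in the case of very small counts (<5"). It does not say whether the threshold applies to observed or expected counts.
- **Section 7, Patient diagnostic and management analysis.** Proportions of diagnoses and management recommendations "will be compared using a chi-square test", in line with that rule.
- **Section 7, Navigation Accuracy.** "The median and standard deviation of the distance will be calculated for both arms", and the arms are then compared with a Student t-test.
- **Section 7, Navigation time.** "The navigation time medians and standard deviations will be calculated for both arms", again followed by a Student t-test.

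No text exempts navigation success from the section 4 rule. No expected success rate is given, and nothing is said about the distribution of time or distance.

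**The concern.** Navigation success is a yes/no result per case. Section 4 sends it to chi-square or Fisher; section 7 sends it to a t-test. An analyst holding the data could follow either and cite the plan, which is the freedom that pre-specification is meant to remove. The choice matters most when failures are few, because that is where section 4 calls for Fisher and where Fisher departs from the t-test. Few failures are plausible: lesions that cannot be localised are an intra-operative exclusion or stopping criterion in section 4.

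The time and distance comparisons have a different fault. A t-test compares means, so it does not test the medians that will be reported, and an SD does not describe spread around a median. This mismatch is present whatever the shape of the data. Whether it also costs power depends on skew.

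**Working it through.** **Inputs.** From the document: 59 per arm, 1:1 allocation, two-sided 0.05 (section 4), and the tests quoted above. Assumed: the example tables, the true success rates, and log-normal times or distances.

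**The plan's own n.** (1.960 + 0.842)² × (0.7×0.3 + 0.9×0.1) / 0.2² = 7.849 × 0.30 / 0.04 = 58.87, so 59 per arm. This reproduces the stated figure.

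**Navigation success, formulas.**
- t-test on 0/1 data: t = d / √(s² × 2/59), with s² the mean of the two sample variances 59p(1−p)/58, and 116 degrees of freedom.
- Fisher, two-sided, equal arms: when one arm has no failures and the other has k, p = 2 × C(59,k)/C(118,k). For 1 v 7 failures, p = 2 × [C(59,8) + 59 × C(59,7)]/C(118,8).
- Smallest expected count: total failures / 2.

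| Successes | d | SE | t | t-test p | Chi-square p (uncorrected) | Fisher p | Smallest observed / expected count |
|---|---|---|---|---|---|---|---|
| 59/59 v 54/59 | 0.0847 | 0.0366 | 2.317 | 0.022 | 0.022 | 0.057 | 0 / 2.5 |
| 59/59 v 55/59 | 0.0678 | 0.0330 | 2.054 | 0.042 | 0.042 | 0.119 | 0 / 2.0 |
| 58/59 v 52/59 | 0.1017 | 0.0457 | 2.224 | 0.028 | 0.028 | 0.061 | 1 / 4.0 |

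In all three, section 4 calls for Fisher on either reading of the threshold. The t-test is below 0.05 and Fisher is above it.

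**How often.** Of the 1,828 distinct non-degenerate tables at 59 v 59, the t-test and the section 4 rule disagree at 0.05 in 16 (threshold read as observed counts) or 8 (expected counts). The t-test and uncorrected chi-square disagree in only 2, for example 45/59 v 53/59 (0.0502 v 0.0497). The conflict therefore lies almost wholly in the Fisher branch. Exact binomial probabilities of disagreement under assumed true rates:
- 95% in both arms: 3.2–3.6% of trials. The t-test rejects in 4.6%, the section 4 rule in 1.0–1.4%.
- 90% v 98%: 14.6–18.5%.
- 90% v 99%: 21.7–23.4%.

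**Time and distance.** Simulated log-normal data, 59 per arm, 1.4-fold difference, 20,000 replicates:

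| Log-SD (assumed) | Power, t-test | Power, Wilcoxon |
|---|---|---|
| 0.3 | about 100% | about 100% |
| 0.5 | 92–93% | 94% |
| 0.8 | 49–50% | 60% |
| 1.0 | 31% | 43% |

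With no difference between arms, the t-test's type I error was 4–5% for log-SDs from 0.3 to 1.2.

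**The case against.** The strongest reply is that little depends on this. Navigation success, time and distance are absent from the primary and the nine secondary objectives and from section 8. No decision and no sample size rests on them. That is correct, and it sets the severity.

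It can also be said that the section 4 rule sits among the diagnostic-yield definitions, and that a specific instruction in section 7 overrides a general one. The rule is worded for proportional data in general, however, and section 7 uses chi-square for its other named proportion comparisons. Even if the specific instruction prevailed, it would drop the plan's small-count safeguard without giving a reason.

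A third reply is that a t-test on 0/1 data is close to uncorrected chi-square, and that the gap in the table is Fisher's conservatism. This also stands. A reader might infer that the t-test inflates false positives; the calculations do not show that.

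A reader might add 57/59 v 51/59 (t-test 0.048, Fisher 0.094) to the examples. Its smallest expected count is exactly 5, so on the expected-count reading chi-square applies (p=0.047) and agrees with the t-test. It is a conflict only on the observed-count reading.

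Finally, a reader might take the choice of medians as evidence that time and distance are skewed. The document does not say so, and at a log-SD of 0.5 or less the choice of test makes almost no difference.

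**Conclusion.** The point holds as a minor inconsistency. One comparison of proportions has two conflicting tests, and two continuous measures have a summary that does not match the test.

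For navigation success, the tests can fall on different sides of 0.05 when failures are few, as in the three tables shown. That scenario is an assumption, and outside sparse tables the practical difference is negligible. It would be tempting to say that the two rules give opposite conclusions. They do not: the direction of effect is the same, and only the significance label changes.

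For time and distance, the mismatch of summary and test is certain. A loss of power is conditional: about 10 to 12 percentage points at assumed log-SDs of 0.8 to 1.0, and close to none at 0.5 or below.

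Nothing here touches the primary analysis or the 59 per arm.

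**What to change.** - **Navigation success.** Delete the t-test and apply the section 4 rule. State there whether the threshold of 5 refers to observed or expected counts. Report the risk difference with a 95% CI.
- **Navigation time and distance.** Make summary and test agree. As the plan chose medians, report median and interquartile range, with a Wilcoxon rank-sum test and a Hodges-Lehmann difference with CI. If means are intended, report mean and SD with a Welch t-test. Either removes the mismatch.

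**Cost.** SAP wording only, with no new data or patients. Under Fisher, navigation success will reach significance less often when failures are few: at assumed true rates of 90% v 98%, the chance of p<0.05 is 45% with the t-test and 27–31% under the section 4 rule.

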- b. The number and frequency of nCLE procedure-related AE/SAE from the start of the procedure until end of 12-month follow-up
- 8. To assess the reproducibility of nCLE criteria to the reference standard. Three nCLE characteristics for the detection of malignancy were identified during Wijmans et al. study [10]:
 - a. Dark enlarged pleomorphic cells;
 - b. Dark cell clusters consist of overlapping cell structures ('dark clumps') and
 - c. Continuous movement of the cells in one direction ('directional streaming').
- 9. To create an nCLE image atlas for malignant characteristics in PPNs.

3. Study Design

This is a randomized, controlled, interventional, comparative prospective multi-center study. In total, a maximum of 118 consecutive patients with a (suspected) PPN who are referred for a diagnostic bronchoscopic (Robotic-guided TBNA) procedure will be considered for enrollment. The estimated duration of the study is 24 months. Patients will be consecutively recruited and randomly assigned to undergo Robotic-guided TBNA (n=59) or Robotic-nCLE-guided TBNA (n=59).

Only patients in the nCLE arm will receive intravenously administered fluorescein before the start of the Robotic procedure. During the nCLE procedure, an 18G needle enters the targeted tissue, followed by an nCLE AQ-Flex™ 19N Confocal Miniprobe™ (Mauna Kea Technologies, France) through the biopsy needle, to obtain real-time imaging. nCLE imaging will be performed in the PPNs with a total estimated time for research measurements of 10 minutes. nCLE imaging will be performed for each sequential TBNA pass/sampling within the lung nodule lesion and each TBNA path cytopathological result will be correlated with the nCLE sequence acquired for that TBNA pass. TBNA sampling will end when sufficient diagnostic material will be found with ROSE (as assessed by the cytopathologist) or when the physician performing the procedure judges that the number of samplings/passes is adequate. ROSE will be performed by a cytopathologist.

4. Study Population

Population (base)

Patients with a PPN referred for diagnostic bronchoscopic/endosonographic workup tissue sampling based on standard (PET-) CT imaging

Inclusion criteria

To be eligible to participate in this study, a study subject must meet all of the following criteria:

- ≥ 21 years of age
- Suspected PPN
- Nodule size in CT between 8 mm and 30 mm (largest dimension)

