nCLE requires the administration of exogenous fluorescent contrast. Minutes before CLE positioning, the patient will be administered 2.5 mL of 10% fluorescein IV. A repeat dosage of 2.5 ml of 10% fluorescein can be provided after 15-30 minutes to a maximum dosage of 5 ml of 10% fluorescein in total. Patients will be monitored for allergic reactions, including anaphylaxis. Fluorescein Sodium can be used as a contrast agent with Cellvizio® I.V.E system with Confocal Miniprobes™ without change of formulation, mode of action, approved dose, or route of administration. Refer to the indications for using the fluorescein to perform the injection or to chapter 1: "Fluorescein Angiography: Basic Principles and Interpretation" of Ryan et al. book on Optical Imaging Technologies [25].

The target area will then be identified on the ultrasound and/or fluoroscopy monitor and accessed in the usual manner per standard of care. Once the nodule is localized, an 18G needle with the Confocal Miniprobe™ inside will be introduced through the bronchoscope's working channel and advanced into a lung nodule. After the puncture, the AQ-Flex™ 19 N Confocal Miniprobe™ will then be advanced through the needle into the nodule. Imaging will take place, which will be evaluated by the physician performing the procedure. The on-site image interpretation will be recorded. The AQ-Flex™ 19 N Confocal Miniprobe™ will be removed, and tissue will be aspirated at the imaging site from the tip of the needle that is still in place. ROSE will be performed by the cytology team per standard of care. If no lesional tissue is identified, then the robot may be repositioned for additional needle passes. For each needle pass, a separate CLE movie will be recorded. Multiple needle passes and nCLE imaging may occur, specifically if no tumor is identified on ROSE. In the case of re-localization of the needle, nCLE imaging may be repeated before further needle aspirations. Duration will be recorded after each pass. Chest ultrasound or fluoroscopy will be performed to evaluate for pneumothorax.

7. Puncture the identified target lesion with the needle per standard of care and usual procedure (the Confocal Miniprobe™ is pre-loaded but retracted)	8. Maintain the needle as straight as possible and parallel to the working channel of the scope. (to limit the retraction of the probe within the working channel) Twist the locking device and the probe back onto the needle
	

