3. Lidocaine 10ml will be orally administered to provide local throat and tracheal anesthesia.
4. The bronchoscope will be introduced into the trachea.
5. After target localization (lung tumor), a guiding needle (FlexNeedle 18G, Broncus Medical) will be introduced in the working channel of the scope and on the placement of the endoscope within the bronchus in proximity to the target, the needle is introduced through the bronchial wall and into the lung tumor using fluoroscopy and r-EBUS guidance.
6. **(research-purposes) nCLE acquisitions will be obtained (only in patients in the ROBOTIC-nCLE-guided TBNA arm) by fitting the optical fiber into the TBNA needle and introducing it in the target lesions under fluoroscopy control.**
7. After the nCLE data is acquired and the probe is retrieved, cytological samples will be conducted following a standard protocol (ROSE).
8. Steps 6 and 7 will be performed for each pass.
9. The bronchoscope will be retrieved.

On completion of each procedure, the patients will be extubated and transferred to the recovery area. All patients will be monitored until discharge per standard institutional clinical protocol. This includes a chest x-ray post-procedure to determine whether the patient has suffered a pneumothorax. In the case of a pneumothorax, the complication will be treated with the institutional standard of care. The risks associated with the procedure are no different from a routine bronchoscopy and biopsy. There is a small increased risk

that a patient may have an allergic reaction to fluorescein. Again, this complication will be treated with the institutional standard of care.

nCLE analysis

Each nCLE-video will be analyzed in a blinded fashion to evaluate nCLE lung nodule and lymph node characteristics. The results of the nCLE video reviews will be compared to the corresponding cytological or histopathological results.

Three blinded raters will review nCLE videos for image quality, lung lesion detection and CLE characteristics.

Training session for CLE raters

nCLE raters with various backgrounds will be trained in the nCLE lung cancer criteria using powerpoint slides, hand-drawn schematics and a preselected set of training videos that had not been used previously. Training slides with hand-drawn nCLE lung cancer criteria schematics will also be provided.

Intra-procedure Interpretation of nCLE

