- Lung zone (peripheral, middle, and proximal thirds)
- Visibility on fluoroscopy (if applicable)
- Positron emission tomography (PET)-positive (yes/no)
- Associated lymphadenopathy
- Distance to closest fissure
- Distance from lesion to pleura
- Pre-procedure probability of malignancy (investigator assessment)

Procedural assessments

- Indication for procedure
- Anesthesia type
- Catheter type
- Procedure duration
- Imaging used (fluoroscopy, PET, radial endobronchial ultrasound [EBUS])
- Ability to successfully navigate to the lesion
- Use of associated tools and type (e.g., access tools, biopsy forceps, cytology brush, aspiration needle)
- Number of lesions biopsied
- Distance between the tip of the locatable guide/nCLE Confocal Miniprobe for each lesion
- Cases in which the operator can successfully navigate to the lung target with Robotic-guidance and Robotic-nCLE guidance, based on investigator self-assessment
- Number of lymph nodes biopsied (if applicable)
- Placement of fiducial markers (if applicable), the type used, indication, and status at follow-up imaging
- Surgical resection, including use of dye marker, the type used, and adequacy for surgical resection
- Diagnosis by both cytologic rapid on-site evaluation (ROSE) and pathology
- Cancer type (primary or metastatic), if applicable
- Cancer stage, if applicable
- Adequacy of sample for molecular testing and mutation type (if applicable)
- Number and type of repeat bronchoscopy procedures or other biopsies
- Other health services (e.g., imaging, transfusion, surgery, emergency room admission, prescriptions) received during admission for the index procedure
- Hospital admission duration
- Adverse events, action taken, relationship to device, and outcome

Follow-up assessment

- All health services (e.g., imaging, transfusion, surgery, emergency room admission, prescriptions) received since the last visit
- Since index procedure, all healthcare services related to lung health (e.g., primary care and specialist visits, hospital, emergency room, oncology, radiology, and pain management).
- All therapeutic and diagnostic procedures and diagnoses related to lung health since the last visit
- Adverse events, action taken, relationship to device, and outcome

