The benefit of study participation is that the results of this study may be significant for future patients. nCLE is a promising safe, minimally-invasive imaging technique that, in conjunction with conventional endoscopic workup procedures, can provide real-time, high-resolution microscopic imaging of tissue characteristics within different organs in reach of bronchoscopy/endosonography. There is little burden related to study participation. After needle placement within the lymph node or lung tumor (standard procedure), we will hold the needle into place to obtain a CLE video.

Fluorescein, a commonly used stain in hospitals, will be administered (only in patients in the nCLE arm). In patients not at risk for allergic reactions to fluorescein (allergic reaction to fluorescein in the medical history), this is safe, and the risk of an adverse reaction is low (1.1 %). The most typical adverse reactions were mild, such as nausea (0.7%) [13]. Based on the fluorescein manufacturer's manual, patients with a known allergy to fluorescein and patients who used a beta-blocker within 24 hours before the intervention, and patients who are pregnant or lactating will be excluded. Based on the literature, we will not exclude patients with a previous reaction to another type of drug than fluorescein, as the literature shows that the incidence rate of an adverse reaction due to intravenous administration of fluorescein in 'special patient groups (such as: above 80 years old, drug allergy history, system disease) was similar to that in the healthy population. The estimated time for a bronchoscopic procedure is 25-35 minutes. The estimated prolonged endoscopy time for nCLE imaging is 10 minutes.

The patient will not notice anything due to the use of midazolam (fentanyl) or Propofol sedation (following standard procedure). Adverse events are not expected. A recent study by Karstensen et al. [28], combined EUS-FNA with nCLE in abdominal lymph nodes and pancreas, and no adverse events occurred during the 30-day follow-up. Also, no adverse events were reported in the study by Wijmans et al. [10] in the same target population. As stated by the hospitals, the standard diagnostic, therapeutic (lobectomy) process, and pathological evaluation, this study will not affect the internal protocol. In conclusion, we believe that the burden and risk associated with participation are negligible.

10. Administrative

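### Navigation time and distance are defined on a guide in one arm and a guide or imaging probe in the other, with no common reference event, so their between-arm tests do not isolate navigation

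*Combined protocol and SAP*

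**What the plan says.** Section 7, Navigation time, defines the measure as "Total time that the locatable guide/ nCLE Confocal MiniprobeTM is used in the subject" during the procedure of either arm. It gives no start point, no stop point and no rule for excluding imaging. Section 7, Navigation Accuracy, says: "Distance between the tip of the locatable guide/nCLE Confocal MiniprobeTM and the targeted lung lesion will be measured for each nodule". It does not say when. Each measure is compared between arms with a Student t-test.

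The matching data item in Section 6, Procedural assessments, reads "Distance between the tip of the locatable guide/nCLE Confocal Miniprobe for each lesion". It adds no timing and omits the second reference point.

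Section 5 describes how the probe is used. Under the standard and study steps, "nCLE acquisitions will be obtained (only in patients in the ROBOTIC-nCLE-guided TBNA arm"; the control arm has no probe. Under the steps during the procedure: "Once the nodule is localized, an 18G needle with the Confocal Miniprobe™ inside will be introduced". After the puncture the probe is advanced into the nodule. Section 3 adds that "nCLE imaging will be performed for each sequential TBNA pass/sampling within the lung nodule lesion", and Section 5 repeats the imaging and sampling steps at every pass.

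On duration, Section 9 says: "The estimated prolonged endoscopy time for nCLE imaging is 10 minutes". The Summary calls 10 minutes a maximum. Section 9 puts a bronchoscopic procedure at 25 to 35 minutes.

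**The concern.** A navigation measure should show how quickly and how closely the operator reached the target. Here the defining instrument includes a device that only one arm has and that comes into use once the target has been found. Followed literally, the rule gives the two arms different quantities under one name.

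The risk is in interpretation. A longer navigation time could be held against nCLE, or a shorter distance credited to it, when the definition produced either. The loss may also be permanent. If neither an arrival time nor a distance before deployment is recorded, the analysis cannot rebuild them. The time logged after each pass does not separate navigation from imaging within the first pass.

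**Working it through.** **Plan's own figure.** The documents give no expected value, SD or power for navigation time or distance, so there is nothing of that kind to reproduce. The only figure borrowed below is the 59 per arm from the sample size section. It reproduces with the unpooled two-proportion formula: (1.960 + 0.842)² × (0.7×0.3 + 0.9×0.1) / 0.2² = 58.87, rounded up to 59.

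**Time: the two readings of the slash.**

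1. *Guide plus probe.* Control time is guide time. nCLE time is guide time plus probe time, and the probe is there to image. Imaging is therefore counted as navigation in one arm only, which lengthens the nCLE arm.
2. *Guide or probe, according to arm.* Control time is guide time. nCLE time is probe time, which starts after localization, so the navigation itself is left out. The nCLE arm could come out longer or shorter.

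The arms are not comparable under either reading. The procedure steps do not describe the locatable guide or say how long it stays in place. Deleting the probe from the definition would therefore not be enough; a stop event is needed.

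**Distance.** Section 5 describes the probe in two positions: retracted about 2 cm inside the needle during needle positioning, and advanced into the nodule after puncture. In the second position the tip-to-lesion distance is near zero by placement. A guide-tip distance in controls is a different quantity. Which moment is meant is not stated.

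**Size of the time component.** Inputs: 10 minutes of added endoscopy time and a 25 to 35 minute procedure (Section 9). 10/35 = 29% and 10/25 = 40%. These are shares of the whole procedure and do not estimate bias in navigation time, for which the documents give no figure.

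**Illustration, first reading only.** Suppose true navigation is identical and imaging adds d minutes to the nCLE arm, with 59 per arm and a two-sided 0.05 test. With SE = SD × √(2/59), the chance of a significant result is Φ(d/SE − 1.96) + Φ(−d/SE − 1.96). For d = 10 and SD = 15: SE = 15 × 0.184 = 2.76, d/SE = 3.62, and the result is 0.95. The SDs are assumptions, and 10 minutes is the top of the range.

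| Assumed SD (min) | d = 2.5 | d = 5 | d = 10 |
|---|---|---|---|
| 5 | 0.78 | >0.99 | >0.99 |
| 10 | 0.27 | 0.78 | >0.99 |
| 15 | 0.15 | 0.44 | 0.95 |
| 20 | 0.10 | 0.27 | 0.78 |
| 25 | 0.08 | 0.19 | 0.58 |

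With one definition and a clock stopped before imaging, d = 0 and the rate is 0.05.

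**The case against.** The strongest reply is that the plan is loosely worded and not biased by design. Four parts of it deserve an answer.

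- *Direction.* A reader might infer that the nCLE arm must show longer time and shorter distance. The documents do not support that. Longer time follows only from summing guide and probe; the by-arm reading leaves the sign open. Shorter distance requires measurement on the deployed probe, which is not stated. The standard needle step also places the needle in the tumor in both arms, so a distance taken at sampling could be near zero in controls too. This part of the reply stands.
- *Size.* The 29 to 40% is tempting as a measure of inflation, but its denominator is the whole procedure and its numerator is an upper estimate. This stands too.
- *Importance.* Neither measure is a listed objective or endpoint. Procedure length is collected separately, and time is logged at each pass. This stands and limits the weight of the point.
- *Legitimacy.* Total device time is a fair measure of the burden of a strategy, and stopping the clock before the probe is deployed excludes what nCLE is meant to add. That is correct, but it argues for reporting device time under its own name, not for testing it as navigation.

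What the reply does not remove is that no section sets a common instrument, a common event or an imaging exclusion.

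**Conclusion.** The point holds in a limited form. As written, the navigation time comparison does not measure the same thing in both arms under either reading of the slash. The distance comparison has no stated moment and is not comparable if the nCLE value is taken on the deployed probe.

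The documents establish neither the direction nor the amount of distortion. If guide and probe times are summed, up to about 10 minutes of imaging enters one arm only. Whether that would dominate the test depends on an SD that the plan does not give.

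The consequence is confined to two supporting comparisons. The primary endpoint, the sample size and the listed secondary objectives are untouched. The wording should still be corrected, because the change is cheap and the missing data may not be recoverable later.

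**What to change.** Amend the data item in Section 6 and the Navigation Accuracy and Navigation time paragraphs in Section 7:

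- **Navigation time**, both arms: bronchoscope insertion to first confirmed localization of the target.
- **Distance**, both arms: guide or catheter tip to lesion at that same moment, before any needle or probe is deployed. Name the instrument, and state both reference points in the data item.
- **Burden**: report nCLE imaging time, total device-use time and procedure time as separate items, labelled procedure burden and not navigation.

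The cost is one added time stamp, one measurement at a fixed moment, and CRF and SAP wording. The downside is that the arms follow the same steps up to localization, apart from fluorescein in the nCLE arm. The navigation comparison should therefore be expected to show little difference and will serve mainly as a check that the arms were navigated alike.
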